(4) Only to be undergone after the last IMP intake by patients discontinuing prematurely from the study after W000 Day10

(5) Results of the exam should be available at this visit, prescription to be done at the previous visit

(6) CGI-I only

(7) Should not be done in case of study discontinuation for consent withdrawal

For further practical details, methods of measurement are provided in sections 7, 8 and 9.

For organisational reasons ASSE, W000, W012, W026, W038 and W052 visits can be split in several days, in order to be able to complete all the study evaluations.

The following recommendations should be followed:

For ASSE:

- ECG, renal ultrasound and laboratory tests could be performed after ASSE visit date but always during the run in period and results must be available for the inclusion visit

For W000, W012, W026, W038, W052:

- CARS2 and CGI study assessments planned at the corresponding visit should be performed on the same day
- efficacy evaluations should be always performed prior to any safety procedure in case both efficacy evaluations and safety procedures have been planned to be performed on the same day,
- parents questionnaires (CARS QPC, SRS2 and quality of life questionnaires) and Vineland scale could be completed on site within 3 days prior to the day of the visit,
- safety evaluations could be done within 7 days prior to the visit date.

Furthermore, taking into account local regulation, it is not compulsory for the patient to attend the visits W000+48h/72h, W000+Day 10, W000+Day17, W026+48h/72h, W026+Day 10 and W026+Day17 on site.

In such a case the following recommendations should be followed:

- The planned blood sampling for electrolytes (Na and K) at these visits will be performed locally.
- A phone contact must be established by the investigator with the patient (when possible) and the parent(s)/ legally representative or caregiver (when applicable) in order to collect any adverse event at these visits.
- vital signs will be collected at home by a study nurse when required.

Special conduct in the case of definitive discontinuation of IMP during the double blind period:

1. Patient will complete the study evaluations planned at WD visit.
2. If IMP definitive discontinuation occurs prior to W012:
 - a. patient will attend W012 visit (if there is at least 2 months between WD and W012) and will be invited to complete CARS2, SRS-2, CGI and AE assessment at W012 as planned in the investigation schedule (Table (4.2.2) 1).

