 - b. patient will attend then W026 visit and will be invited then to complete CARS2, SRS-2, CGI and AE assessment at W026 visit as planned in the investigation schedule (Table (4.2.2) 1).
3. If IMP definitive discontinuation occurs between W012 and W026:
 - a. patient will attend W026 (if there is at least 2 months between WD and W026) and will be invited to complete CARS2, SRS-2, CGI and AE assessment at W026 as planned in the investigation schedule (Table (4.2.2) 1).

In such a case, CARS2, SRS-2, CGI evaluations and AE assessments at W012 and W026 will be completed ONLY if the patient who has definitively discontinued the IMP during the

double blind period, does not require an important modification on his/her current background medical care (see section 5.6.1.).

The conduct in the case of definitive discontinuation of IMP during the double blind period is summarized in the Table (4.2.2) 2.

Table (4.2.2) 2 - Conduct in case of definitive discontinuation of IMP during the double blind period without study withdrawal

Visit (when IMP is definitely discontinued)	WD (to be performed)	W012 (to be performed)	W026 (to be performed)	Wend (to be performed)
D017	x	x	x	NA
W004	x	x	x	NA
W008	x	NA	x	NA
W012	x	NA	x	NA
W016	x	NA	x	NA
W020	x	NA	NA	X
W026	x	NA	NA	X

NA: Not applicable

The maximum total volume of blood collected per participant during the study will be 34 mL. See Table (4.2.2) 3

Table (4.2.2) 3 – Volume (mL) of blood collected per participant during the study

	ASSE	W000 + 48/72h	W000 + Day 10	W000 + Day 17	W004	W012	W026
Haematology	1					1	1
Biochemistry	4					2.5	2.5
Serology							
Pharmacokinetic						1	1
Na/K monitoring	1	1	1	1	1	1	1
TOTAL volume (mL) per visit	6	1	1	1	1	5.5	5.5
	W026 + 48/72h	W026 + Day 10	W026 + Day 17	W030	W038	W052	
Biochemistry					2.5	2.5	
Haematology					1	1	
Na/K monitoring	1	1	1	1	1	1	
TOTAL volume (mL) per visit	1	1	1	1	4.5	4.5	
TOTAL volume (mL) per participant	34						

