5.6. Participant withdrawal

5.6.1. Withdrawal criteria

Premature discontinuation of IMP during the double blind treatment period (W000-W026) does not mean that the participant prematurely stops the participation in the study.

In the case of premature discontinuation of IMP during the double blind period and, if the patient does not require an important modification on his/her current background medical care, he/she will be invited to complete CARS2, SRS-2, CGI evaluations and AE assessment for W012 (if discontinuation occurs prior to W012) and W026 visit as planned in the investigation schedule (Section 4.2.2).

Important modification of current medical care is defined as follows:

- *Newly initiated formal behavioural, cognitive or cognitive-behavioural therapy*
- *Increase/decrease weekly prescribed hours >25% of behavioural, cognitive or cognitive-behavioural therapy*
- *Newly initiated or recently changed pharmacotherapy:*
 - o *Introduction of a psychotropic medication (considered as forbidden in the study, section 6.3)*
 - o *Introduction or dose increase of an antipsychotic*
 - o *Introduction or dose increase of ADHD treatment*

The following criteria will lead to a premature discontinuation of IMP:

- Serum potassium levels < 3mEq/L
- Any suicide attempt, whatever its severity
- High suicidal risk, according to investigator's judgment or with a suicidal ideation of 4 or 5 on C-SSRS-C
- Nephrocalcinosis observed at the renal ultrasound
- Occurrence of seizure(s)
 - o in a patient without any medical history of seizure.
 - o or in a patient with a medical history of seizure if this require any modification of the on-going anti-epileptic treatment.
- Any symptoms or signs of potential renal function failure.
- eGFR $\leq 80\text{mL}/\text{min}/1.73\text{m}^2$ (estimated glomerular filtration rate, Schwartz formula 2009).
- Clinically relevant nephropathy according to investigator's clinical judgment (based on broader sources including risk factors, medical history, clinical examination and biological parameters).
- Clinically relevant hypercalciuria.

In case of abnormal urinary calcium/creatinine ratio that may be the expression of a clinically relevant hypercalciuria, a retest should be performed as soon as possible. Based on these results, the investigator should have a discussion with the local paediatric nephrologist in order to assess whether it corresponds to the presence of a clinically

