10. STATISTICS

10.1. Determination of sample size

The sample size was estimated to meet the primary endpoint defined as the change in CARS from baseline to 6 months using a two-sided Student's test.

With a total of 170 patients, statistical significance should be established with a power of 90% and a type-one error of 0.05 for an effect size of 0.5 between groups.

Assuming around 15% prematurely withdrawal rate, the total number of patients to be included is 200.

Missing data will be imputed using a reference based multiple imputation with a jump-to-reference approach or a standard multiple imputation depending on the reasons of withdrawal. Simulations were carried out to evaluate the impact of this procedure on power under various scenarios. The results on 1000 simulations have shown that power does not drop under 80% in the worst case scenario.

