3.4.2.3. Supplementary analyses

- Treatment policy estimand:

The primary analysis will be repeated for the primary endpoint using all CARS2 values reported regardless of occurrence of treatment discontinuation.

In case of CARS2 values are still missing, the same imputation process as in the primary analysis will be performed for these individuals.

- Hypothetical estimand based on Mixed-effects Model for Repeated Measures

A Mixed-effects Model for Repeated Measures (MMRM) (see Appendix 5.1.3) using the longitudinal data at each planned post-baseline visit of the double-blind period (W004, W012 and W026) will be performed as if patients had continued their randomised treatment. In this analysis, all data occurring after all intercurrent events will be considered as missing. The comparison associated with the analysis will be the contrasts between Bumetanide and placebo for the change from baseline to W026 of the CARS2 total score. The model will include the fixed, categorical effects of country, gender, treatment, visit, treatment by visit interaction, country by visit interaction and gender by visit interaction as well as the continuous, fixed covariates of baseline and visit-by-baseline interaction:

*MMRM: change at each visit = baseline country gender treatment visit treatment*visit baseline*visit country*visit gender*visit [4]*

Statistical elements: the following elements will be provided in a summary table:

- Estimate (standard error) of the difference between adjusted treatment arm means.
- Two-sided 95% CI of the estimate.

- W012 analysis:

The primary analysis will be repeated for the CARS2 total score expressed in term of change from baseline to W012.

- CARS2 responders analysis:

Definition:

CARS2 responders will be defined as patients having an improvement of at least 4.5 points in the CARS2 total raw score as compared to baseline (Jurek *et al.*, 2021).

Main Analysis:

CARS2 responders at W012 and at W026 will be analysed using a logistic regression model with the fixed categorical effect of treatment, country and gender.

Note: In case of a complete separation of data (zero cell count in a treatment group), only descriptive statistics will be provided. In case of quasi-completed separation of data, a logistic regression with penalized maximum likelihood will be used (see Appendix 5.1.4).

Missing data handling:

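### The W026 CARS2 is withheld from children who stop study drug and need a change in care, and late stoppers' CARS2 has no SAP rule, so the treatment-policy analysis falls back on the primary imputation for them

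*Protocol*

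**What the plan says.** **Collection after a stop.** Protocol 4.2.2 first sends every child who definitively stops study drug in the double-blind period to WD. It then states that CARS2, SRS-2, CGI and adverse-event assessments at W012 and W026 "will be completed ONLY if the patient who has definitively discontinued the IMP" needs no important modification of background care. Section 5.6.1 carries the same condition and defines it: new behavioural or cognitive therapy, a change of more than 25% in weekly therapy hours, a forbidden psychotropic, or the start or increase of an antipsychotic or ADHD drug.

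**Timing.** For stops between W012 and W026, 4.2.2 says "patient will attend W026 (if there is at least 2 months between WD and W026"). A parallel condition applies to W012: "if there is at least 2 months between WD and W012". Section 5.6.1 mentions the visits "for W012 (if discontinuation occurs prior to W012) and W026 visit as planned", then refers back to 4.2.2. Table (4.2.2) 2 requires W026 for stops from D017 to W016 and marks Wend not applicable. For stops at W020 and W026 it does the reverse.

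**Other CARS2 occasions.** Section 7.2 and the investigation schedule place a CARS2 at WD (after W000+Day10) and at Wend. Section 4.2.1 puts Wend 6 weeks after treatment stops.

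**Analysis.** SAP 3.4.2.3 plans a supplementary treatment-policy analysis "using all CARS2 values reported regardless of occurrence of treatment discontinuation". Values still missing are imputed as in the primary analysis. SAP 3.4.2.1 names W4, W12 and W26 as the imputation time points.

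**The concern.** A treatment-policy estimand asks how children fare after randomisation whatever happens to their treatment. A change of care after stopping drug is part of what it should capture. The protocol makes that change a reason not to collect the outcome.

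The omission is unlikely to be neutral. Section 5.6.1 stops study drug when a new condition requires a forbidden medication, and for lack of efficacy. The first can itself be an important care change under the protocol's definition, and the second could plausibly lead to one. After the stop, Section 6.5 leaves treatment to the physician. The children whose W026 score is withheld may well be those doing worst.

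This matters because the treatment-policy analysis is the only planned between-group model of W026 CARS2 built to use off-treatment scores. The primary analysis and the MMRM both set them to missing. The responder analysis reuses the primary imputations, and the one listed sensitivity analysis only drops country and gender. Where the off-treatment score was never collected, the treatment-policy analysis repeats the assumption that it could otherwise help to check.

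**Working it through.** **1. The plan's own figure.** Protocol 10.1 uses 90% power, "a type-one error of 0.05 for an effect size of 0.5 between groups", "using a two-sided Student's test".
- Per arm: n = 2(z₀.₉₇₅ + z₀.₉₀)²/d² = 2(1.960 + 1.282)²/0.5² = 84.1, rounded up to 85, so 170 in total. The t distribution gives 85.03 per arm, and power of 89.99% at 85.
- Inflation: 170/(1 − 0.15) = 200.

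The sample size reproduces and is not in question. It supplies one input: 0.15 × 200 = 30 planned premature withdrawals.

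**2. What is scheduled after each stop**, from Table (4.2.2) 2, with Wend at stop + 6 weeks:

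| Stop at | Weeks to W026 | W026 visit | Wend | Scheduled CARS2 after stop if care changes |
|---|---|---|---|---|
| D017 | about 24 | yes | no | WD only |
| W004 | 22 | yes | no | WD only |
| W008 | 18 | yes | no | WD only |
| W012 | 14 | yes | no | WD only |
| W016 | 10 | yes | no | WD only |
| W020 | 6 | no | yes, about W026 | WD and Wend |
| W026 | 0 | no | yes, about W032 | WD (about W026) and Wend |

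Up to W016 without a care change, W026 is scheduled. Up to W016 with one, the table leaves nothing after WD. From W020 a CARS2 exists near W026 in either case.

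**3. What the SAP does with each group.**
- *No W026 value:* jump-to-reference for bumetanide stops due to adverse event or lack of efficacy; same-arm missing-at-random imputation for all others. This is the primary rule.
- *WD or Wend value near W026:* no rule links it to W026. The only stated analysis of Wend CARS2 is descriptive, in children dosed in the open-label period (SAP 3.4.2.3). Children who stopped for good in the double-blind period would not normally be among them.

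**4. Size.** Assumptions, none of them in the documents: all 30 stop drug but stay in the study, and stop times are uniform over 26 weeks. The share falling under the late rule depends on how 2 months is read:
- from W020, as in the table: 6/26 = 23.1%, and 0.231 × 30 = 6.9
- under 8 weeks: 8/26 = 30.8%, and 0.308 × 30 = 9.2
- under 61 days: 61/182 = 33.5%, and 0.335 × 30 = 10.1

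The share of the remaining children who need a care change is unknown. With c for that share, the number without a W026 visit is 30 × [late + (1 − late) × c]:

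| c | Late 23.1% | Late 30.8% | Late 33.5% |
|---|---|---|---|
| 0 | 6.9 | 9.2 | 10.1 |
| 25% | 12.7 | 14.4 | 15.0 |
| 50% | 18.5 | 19.6 | 20.0 |
| 75% | 24.2 | 24.8 | 25.0 |

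That is about 3.5% to 12.5% of 200. The late part counts missing W026 visits, not missing CARS2 scores.

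**The case against.** The best defence is that little rests on this analysis. The primary analysis discards post-discontinuation scores by design, so it does not change. The treatment-policy analysis is supplementary and carries no p-value (SAP 3.4.1). Every child stays in the Randomised Set. Some imputation would be needed even with ideal follow-up. All of this stands, and it limits the weight of the point.

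The link between care change and poor outcome is an inference. The definition also covers a fall of more than 25% in therapy hours. The link is plausible from the stopping criteria but not documented.

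A child whose care changes might be handled as leaving the study, in which case Section 4.2.1 would bring a Wend visit. For stops up to W016 that visit falls at W022 or earlier, so it does not replace W026.

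A reader might also infer more than the documents support:
- *That late stoppers have no CARS2.* They have it at WD and Wend; a rule for using it is what is missing.
- *That the SAP excludes those values.* It is silent. The treatment-policy text speaks of all reported values, and the list of time points belongs to the imputation step.
- *That 5.6.1 contradicts the 2-month rule.* It omits the condition but defers to 4.2.2, which contains it.
- *That requiring W012 after a W004 stop breaks the rule.* Only if 2 months means 61 days. The 3-month analysis in Protocol 10.2.2.4.2 is the W012 analysis in the SAP, and on that scale 8 weeks is 2 months.
- *That adverse events go unreported after a care change.* Section 8.9.1 keeps reporting in force for children who stop drug but remain in the study. Only the scheduled assessment is conditional.

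**Conclusion.** The concern holds for the care-change condition. After stops up to W016, that condition removes the W026 CARS2 in a way that plausibly depends on outcome, and the table offers no later score. For these children the treatment-policy estimate rests on the primary analysis's imputation and cannot check it. For late stops the gap is narrower: a score is scheduled at or near W026, and the SAP lacks a rule to use it.

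The size cannot be fixed from the documents. The 7 to 10 W026 visits removed by the late rule are an upper range, because children lost to follow-up or withdrawing consent would have no W026 under any rule. The care-change number depends wholly on an unknown share. The conclusion about the care-change condition rests on the protocol wording and does not depend on these counts. The primary result, the sample size and the Randomised Set are untouched, so this is a should-fix point about a supplementary estimand.

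**What to change.** 1. Protocol 4.2.2 and 5.6.1: remove the care-change condition for the W026 CARS2. Invite every discontinuer who stays in the study and has not withdrawn consent.
2. Record the care change, with its date, as an intercurrent event, so that its role can be described.
3. SAP 3.4.2.3: define an analysis window within which a WD or Wend CARS2 near W026 serves as the W026 value in the treatment-policy analysis. A W020 stop, with Wend at about W026, is the clear case.
4. Make 4.2.2, Table (4.2.2) 2 and 5.6.1 say the same, and state what 2 months means in days or weeks.

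This changes data collection and analysis only, not how any child is treated. The cost is protocol and SAP wording plus about one extra assessment visit for a small number of children. The SAP window needs no new data.

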4.3. Measures to minimise bias

The following measures have been taken to avoid biases:

- This is a randomised, placebo-controlled study carried out in double-blind conditions. Active treatment (bumetanide) and placebo oral formulations will have the same appearance and the same taste.
- An Interactive Response System (IRS) will be used for the treatment allocation: bumetanide or placebo will be assigned at inclusion (W000) by balanced (ratio 1:1) randomisation, with stratification on the country and on the patient sex. The structure responsible for designing and constructing the randomisation list in blind will be the Center of Excellence Methodology and Valorisation of Data of I.R.I.S.
- Investigators in charge of diagnosis should have a deep knowledge on the Autism Diagnostic Observation Schedule, second edition (ADOS-2) and Autism Diagnostic Interview - Revised (ADI-R) diagnostic tools.
- Training sessions on assessment scales will be organized for the investigators prior to their involvement and their participation will be mandatory.
- In order to maintain the double-blind conditions, the main efficacy criterion (CARS2) will be assessed by an independent rater. This rater will not be involved with any aspect of medical management of the patient and will not have access to patient data. The independent rater will be instructed not to discuss what adverse event (if any) the patient is experiencing from his/her medication. Prior to being examined by the independent rater, patients and parent/legal representative(s) or caregiver (when applicable) will be instructed not to discuss what (if any) adverse event patient may be experiencing. As far as possible same independent rater will assess CARS2 for a given patient all along the study (from W000 till W052 and at least till W026) and, when possible, all the patients for a given site.
- The laboratory parameters will be performed by a central laboratory in order to centralize and harmonise the data, with the exception of Na^+/K^+ which should be monitored always locally when the patient is under treatment to quickly manage Potassium Supplementation when needed.
- In addition to immediate local safety reading for safety reasons, a centralized assessment will be performed for each ECG (central reading reports for ECG overrule local reading for inclusion/exclusion/withdrawal criteria).
- Samples for pharmacokinetic analysis will be sent to the central laboratory and transferred to the assay centre Cephac for analysis using a validated assay method. The assay centre in charge of bumetanide measurement will be provided with the treatment codes so that only samples from patients being treated with bumetanide will be assayed. The results of bumetanide blood concentration will be transferred from Cephac to the PK department of I.R.I.S. before the clinical database [associated to statistical analysis (ASSE W026 period)] is locked and blind is broken. In order to prevent a blind break, administration and sample times will only be recorded on the requisition form and not on the electronic Case report Form (e-CRF). The central laboratory will capture data of the requisition form and will calculate the time after dose. Real time after dose will be transferred to Cephac for analyses. The PK department will receive only recoded data (recoded patient number). PK results

from Cephac and requisition form data from the central laboratory will be transferred to the I.R.I.S. Data Management department only after blind is broken.

- The main analysis of the study concerns the double blind period from W000 to W026 visit. The blind will be broken as soon as all efficacy and safety data collected during this period are available and the mandatory steps defined in section 14.2 “Data Management” have been performed. Nevertheless, although the blind will be broken centrally before the end of the study, neither the investigators, nor the raters, nor the patients/legal representatives/caregivers, nor the parents, nor the local project managers, nor the monitors will be informed of the study treatment taken during the double-blind treatment period and of the study results of the first period before the database lock for the whole study period (W000-W052).

4.4. Study products and blinding systems

4.4.1. Products administered

In the frame of this protocol, IMPs are S 95008 (at the dose of 0.5 mg/bid) and placebo.

The IMP dispensed will be an oral formulation (solution of 0.5mg/mL of bumetanide or a placebo solution with the same appearance and taste). This solution will be administered with a 1 mL graduated pipette.

All the patients will take orally the study treatment twice a day:

- **in the morning at wake up**
- **in the afternoon, 3 hours before going to bed at the latest.**

In any case the study treatment must be taken around 15 minutes before any food intake.

The pipette containing the oral solution should be administered preferably into the mouth of the patient.

The volume of the oral solution will be adapted according to a body-weight basis for patients with a weight lower than 25Kg (See [Appendix 1](#)).

An adaptation of the oral solution volume according to the weight of the patients will be performed during the study at visits W012, W026 and W038.

Each treatment dispensed throughout the study will be similar so that it is not possible to differentiate the study treatments (bumetanide or placebo).

- **From selection to inclusion:** patients will not take IMP.

- **During the double-blind period of 6 months:** from W000 (inclusion) to W026 visits
The first study treatment intake will be on the day of the inclusion visit in the afternoon, 3 hours before going to sleep at night at the latest.

➤ Patients with a body weight < 25 kg:

Patients randomised in the bumetanide arm: from W000 to W026 visits will take 0.02 mg/kg of bumetanide twice a day i.e.:

- volume of bumetanide oral solution (mL) = 0.04 x body weight (kg) in the morning at wake-up,
- volume of bumetanide oral solution (mL) = 0.04 x body weight (kg) in the afternoon, 3 hours before going to bed at the latest.

Patients randomised in the placebo arm: from W000 to W026 visits will take placebo solution twice a day i.e.:

- the volume of placebo oral solution (mL) = 0.04 x body weight (kg) in the morning at wake-up,
- the volume of placebo oral solution (mL) = 0.04 x body weight (kg) in the afternoon, 3 hours before going to bed at the latest.

➤ Patients with a weight \geq 25kg:

Patients randomised in the bumetanide arm: from W000 to W026 visits will take 0.5mg of bumetanide twice a day i.e.:

- 1ml of bumetanide oral solution in the morning at wake-up,
- 1ml of bumetanide oral solution in the afternoon, 3 hours before going to bed at the latest.

Patients randomised in the placebo arm: from W000 to W026 visits will take placebo solution twice a day i.e.:

- 1ml of placebo oral solution in the morning at wake-up,
- 1ml of placebo oral solution in the in the afternoon, 3 hours before going to bed at the latest.

- **During the open label treatment period of 6 months:** from W026 to W052 visits

All patients will be treated by bumetanide.

➤ For patients with a weight $<$ 25 kg:

From W026 to W052 visits, patients will take 0.02 mg/kg of bumetanide twice a day:

- the volume of bumetanide oral solution (mL) = 0.04 x body weight (kg) in the morning at wake-up,
- the volume of bumetanide oral solution (mL) = 0.04 x body weight (kg) in the afternoon, 3 hours before going to bed at the latest.

➤ For patients with a weight \geq 25kg:

From W026 to W052 visits, the patients will take 0.5 mg of bumetanide twice a day, in the morning at wake-up and in the in the afternoon 3 hours before going to bed at the latest i.e.:

- 1ml of bumetanide oral solution in the morning at wake-up,
- 1ml of bumetanide oral solution in the afternoon, 3 hours before going to bed at the latest.

- **During the Follow-up period,** the patients will not be treated with IMP.

Table (4.4.1) provides a description of the IMP(s).

Table (4.4.1) 1 – Description of the IMPs

	S95008	Placebo
Pharmaceutical form	Oral solution	Oral solution
Unit dosage	0.5 mg/mL 1 mL corresponds to 0.5 mg of bumetanide	0
Appearance, colour	Colourless to pale yellow solution	Colourless to pale yellow solution
Composition	Bumetanide 0.5 mg Sodium methyl parahydroxybenzoate Sodium propyl parahydroxybenzoate	Sodium methyl parahydroxybenzoate Sodium propyl parahydroxybenzoate

Table (4.4.1) 2 and Table (4.4.1) 3 provide a description of the packaging of the IMPs.

Table (4.4.1) 2 – Description of packaging of the double-blind IMP

Number of units of the pharmaceutical form per primary packaging	60mL of S95008 or placebo oral solution in an amber glass bottle with polypropylene / low density polyethylene child-resistant and tamper-evident cap
Number of primary packaging per secondary packaging	2 bottles of S95008 or placebo per box with 2 graduated pipettes of 1mL
Number of secondary packaging per participant and per treatment period	1 box given per visit with allocation by the IRS

Table (4.4.1) 3 – Description of packaging of the open IMP

Number of units of the pharmaceutical form per primary packaging	60mL of S95008 oral solution in an amber glass bottle with polypropylene / low density polyethylene child-resistant and tamper-evident cap
Number of primary packaging per secondary packaging	2 bottles of S95008 per box with 2 graduated pipettes of 1mL
Number of secondary packaging per participant and per treatment period	1 box given per visit with allocation by the IRS

The labelling of packages complies with the regulatory requirements of each country involved in the study, as well as the recommendations in [Appendix 18](#) of the European Guide to Good Manufacturing Practice.

